Appendix table: Baseline characteristics for responders vs non-responders for each time-point.

Variable	Responder 3 mo (n)	Non-responder 3 mo	Responder 6 mo (n)	Non-responder 6 mo (n)	Responder 12 mo (n=)	Non-responder 12 mo (n=)
Sociodemographic variables						
Age, median (IQR)						
Female, n (%)						
Married or living with partner, n (%)						
Education level high, n (%)						

General health variables

Health-related quality of life (SF-36), median (range)

Physical component score
Mental component score

Hazardous alcohol consumption (AUDIT-C), n (%)

Smoking status, n (%)

Current smoker
Smoked previously
Never

Falls efficacy (FES-I), median (range)

Back pain history and characteristics of current episode

First healthcare provider

General practitioner
Physical therapist
Chiropractor

History of back pain, n (%)

Using pain medication, n (%)

Sleep problems weekly due to back pain, n (%)

Back pain (NRS 0-10), median (range)

Disability (RMDQ 0-24), median (range)

Duration of current episode, n (%)

0 – 6 weeks
6 weeks – 3 months
> 3 months

Psychological variables

Kinesiophobia (FABQ-PA 0-28), median (range)

Depression (CES-D 0-60), median (range)

Pain catastrophizing (PCS 0-52), median (range)

Back beliefs and attitudes (BBQ 9-45), median (range)

Expectations of back pain next 3 months (figure?), n (%)

Fully recovered
Much better
No change or worse

Psychosocial risk profile (SBT)

Low risk
Medium risk
High risk

Clinical variables

Pain with active movements of the back, n (%)

Positive radiculopathy diagnostic rule, n (%)

Two or more red flags, n (%)

Physical performance (BPS), median (range)

Functional mobility (TUG), median (range)

SF-36, Short Form health survey 36; AUDIT-C, alcohol use disorders identification test, score ≥ 3 for women and ≥ 4 for men ; FES-I, Falls Efficacy Scale – International; NRS, numeric rating scale; RMDQ, Roland-Morris Disability Questionnaire; FABQ-PA, Fear-Avoidance Beliefs Questionnaire – Physical Activity; CES-D, Center for Epidemiological Studies – Depression; PCS, Pain Catastrophizing Scale; BBQ, Back Beliefs Questionnaire; SBT, Start Back Tool; BPS, Back Performance Scale; TUG, Timed Up-and-Go.

*Comorbidities measured with Self-administered Comorbidity Questionnaire and a question on osteoporosis.

[figure not shown]
Prevalence of each comorbidity:

Table: Prevalence of each comorbidity at baseline

Comorbidity	N	%
Heart disease		
High blood pressure		
Lung disease		
Diabetes		
Ulcer or stomach disease		
Kidney disease		
Liver disease		
Anemia or other blood disease		
Cancer		
Depression		
Osteoarthritis		
Rheumatoid arthritis		
Osteoporosis*		
(Other non-prespecified comorbidities....)		

All comorbidities measured by Self-Administered Comorbidity Questionnaire

Example figure presenting clinical course, from van der Gaag et al (3):

Proportion of number of comorbidities among patients at baseline, example from Rundell et al (29):

[figure not shown]

Figure 1. Proportion for number of additional pain sites among those with persistent back pain.

RMDQ middle value presented at each time point, presented based on number of comorbidities (29):

Table: Unadjusted RMDQ score at each timepoint in total cohort and by number of comorbidities

	Baseline	3 months	6 months	12 months
Total cohort	Xx	Xx	Xx	xx
No. of comorbidities				
0	Xx	Xx	Xx	xx
1				
2				
3				
4				
5				
6				

RMDQ = Roland-Morris Disability Questionnaire

Association between comorbidities and disability during 1-year follow-up:

Table: Estimates from **mixed model(XX)** of effect of comorbidities on RMDQ score during 1 year of follow-up

	β	95% CI	R²
Comorbidities~			
Covariates			
Comorbidities w/covariates*			

RMDQ = Roland-Morris Disability Questionnaire

~unadjusted effect estimate

*adjusted for time, age, gender, education level, smoking status, hazardous alcohol consumption, back pain duration, probable radicular leg pain, (recruitment profession?)

^adjusted for age, gender, education level, smoking status, hazardous alcohol consumption, back pain duration, probable radicular leg pain, (recruitment profession?)

References

3. van der Gaag WH, Enthoven WTM, Luijsterburg PAJ, van Rijckevorsel-Scheele J, Bierma-Zeinstra SMA, Bohnen AM, et al. Natural History of Back Pain in Older Adults over Five Years. *The Journal of the American Board of Family Medicine*. 2019;32(6):781-9.

Prognostic models are a way of providing individual prognosis, using a standardized measurement tool (6). These models combine relevant prognostic factors to try to give an accurate prediction on the individual's prognosis (6). Most previous prognostic models or screening tools for back pain are developed for younger adults (7-11). Only one study has developed prognostic models for use in older adults with back pain (12). This study, performed in the Back Complaints in the Elders (BACE) – Netherlands study, found that a combination of biopsychosocial factors was able to accurately predict persistent back pain, persistent disability and persistent self-reported non-recovery (12). This model has yet to be externally validated, which is a crucial step in prognostic model research (13, 14). The BACE consortium, where research groups from different countries use similar methods and measurement tools to study back pain in older adults in primary care (3), offers an ideal setting for external validation of these prognostic models.

Study aim

The aim of this study is to externally validate three clinical prediction models for non-recovery from a new episode of back pain in older adults. If model performance is poor, the secondary aim is to recalibrate or update the models.

Here we present the study's Statistical Analysis Plan (SAP), which details the analysis steps for the external validation, to minimize the risk of data selection bias and data-driven interpretation of results.

Study design and method

Study design

BACE-N is based on the previously published BACE study protocol from the BACE international consortium (3). The BACE-N protocol has been published elsewhere (ClinicalTrials.gov Identifier: NCT04261309).

The BACE-N study is a prospective observational cohort study with a 2-year follow-up time. Patients are followed up after 3, 6, 12 and 24 months. This article will use data from baseline, 6 and 12 months of follow-up, in line with the original models developed in the BACE Netherlands study. The design of the current study was informed by the framework PROGnosis RESearch Strategy (PROGRESS), which is a framework for ensuring and enhancing the quality of prognostic studies (15). In particular, this is a PROGRESS type 3 study (6). Reporting will be according to the Transparent Reporting of a multivariable

prediction model for Individual Prognosis Or Diagnosis (TRIPOD) statement for prediction studies (16).

Study population

Variables

Outcome measures:

Similarly to the development study (12), non-recovery is defined for three different outcomes:

- Persistent disability: A score of $\geq 4/24$ on the Roland-Morris Disability Questionnaire (RMDQ) at both 6 and 12 months (17, 18). The RMDQ ranges from 0, no disability, to 24, maximum disability.
- Persistent back pain: A score of $\geq 3/10$ on the Numeric Rating Scale (NRS) at both 6 and 12 months. The NRS ranges from 0, no pain, to 10, worst maximal pain.
- Persistent self-reported non-recovery: A score of ≥ 3 on a 7-point Global Perceived Effect (GPE) scale at both 6 and 12 months. GPE scores were:
 1. Full recovery
 2. Much better
 3. Somewhat better
 4. No change
 5. Somewhat worse
 6. Much worse
 7. Worse than ever

Prognostic factors:

In the development study there were 45 potential predictors. After an extensive literature review, consensus meetings, and sample size calculation, 14 candidate predictors were selected:

Table 1: Candidate prognostic factors from development study.			
Prognostic factor	Measurement level	Measured with	Parameters in model
Age	Continuous		1
Sex	Binary		1
Chronic duration of current episode of back pain	Binary	Duration >3 months at baseline	1
Back pain intensity in the past week	Continuous, 0-10	NRS	1
Back-related disability	Continuous, 0-24	RMDQ	1
Recent episode of back pain	Binary	An episode of back pain within the past 6 months, for which they did not seek care	1
Musculoskeletal comorbidity	Binary	Modified Dutch version of SCQ	1
Radiating pain to the leg	Binary	Presence of radiating leg pain in either or both leg(s)	1
Spinal morning stiffness longer than 30 minutes	Binary	Modified KOOS-question 6a	1

Pain during spinal rotation	Binary	Pain with rotation of the upper body during clinical examination	1
Expectations of recovery	Binary.	Likert scale ranging from 1, “fully recovered” to 5, “worse than ever”. Dichotomized into “expecting improvement” and “not expecting improvement”.	1
Depressive symptomatology	Continuous, 0-60	CES-D	1
Kinesiophobia	Continuous, 0-28	FABQ-PA	1
Pain catastrophizing	Continuous, 0-52	PCS	1
NRS; Numeric rating scale, RMDQ; Roland-Morris Disability Questionnaire, SCQ; Self-administered Comorbidity Questionnaire, KOOS; Knee injury and Osteoarthritis Outcome Score, CES-D; Center for Epidemiological Studies – Depression, FABQ-PA; Fear-Avoidance Beliefs Questionnaire – Physical Activity subscale, PCS; Pain Catastrophizing Scale.			

The published clinical prediction models:

The penalized models from the development samples are as follows:

Persistent back pain = $-4.23 + 0.03*Age + 0.73*Chronic\ duration + 0.23*Back\ pain\ intensity - 0.10*Back\ pain\ intensity\ (cubic)\ spline + 0.07*Disability + 0.71*Recent\ episode + 0.38*Spinal\ morning\ stiffness + 0.42*Pain\ during\ spinal\ rotation - 0.79*Recovery\ expectation$

Persistent disability = $-5.97 + 0.04*Age + 0.63*Chronic\ duration + 0.32*Disability - 0.17*Disability\ (cubic)\ spline + 0.40*Recent\ episode + 0.52*Musculoskeletal\ comorbidity + 0.52*Spinal\ morning\ stiffness - 0.83*Recovery\ expectation + 0.08*Depressive\ symptomatology - 0.08*Depressive\ symptomatology\ (cubic)\ spline + 0.02*Pain\ catastrophizing$

Self-reported non-recovery = $-3.46 + 0.03*age + 0.60*Chronic\ duration + 0.13*Disability - 0.07*Disability\ (cubic)\ spline + 1.11*Recent\ episode + 0.36*Pain\ during\ spinal\ rotation - 0.95*Recovery\ expectation$

Changes to candidate prognostic factors and spline terms from development to validation

The development study used a modified version of the Self-Administered Comorbidity Questionnaire (SCQ) which was unavailable at the time of designing the external validation study. Thus, the validation study uses a Norwegian version of the original SCQ.

Due to using different versions of the SCQ, we are unable to replicate the exact measurement of “musculoskeletal comorbidity” in the validation study. Thus, we will exchange this factor

with “comorbidity” measured with the SCQ as a binary variable with cut-off at ≥ 1 comorbidity.

Unfortunately, details on the cubic spline terms in the published original models were unavailable in the manuscript, and sufficient details from the development of the spline terms were unavailable to the authors of this SAP. This means that we are currently unable to replicate the spline terms from the development models in the external validation sample. Sufficient details on the spline terms could become available at a later time and may thus be incorporated before submission of the article based on these analyses.

Finally, there was a slight difference in wording for the prognostic factor “Spinal morning stiffness”. In the Netherlands, patients were asked to indicate if the stiffness lasted longer than 30 minutes, whereas in Norway, they were asked to indicate if it lasted longer than 60 minutes.

Sample size calculation

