The prognostic factor of interest is comorbidity measured at baseline with a modified version of the Self-administered Comorbidity Questionnaire (SCQ) (19). The original questionnaire measures 13 pre-specified comorbidities, and 2 non-specified. The item “back pain” has been removed for this study and replaced with an additional non-specified item. Thus, the count of comorbidity ranges from 0-15. The diseases listed are: Heart disease, high blood pressure, lung disease, diabetes, ulcer or stomach disease, kidney disease, liver disease, anemia or other blood disease, cancer, depression, osteoarthritis, rheumatoid arthritis and up to 3 non-specified comorbidities. The SCQ measures comorbidities on three levels: 1) Do you have the problem? 2) Do you receive treatment for it? 3) Does it limit your activities? All levels are answered on a dichotomous yes/no level, and you only answer level 2 and 3 if you have answered “yes” on level 1. An individual can receive a maximum of 3 points for each medical condition: 1 point for the presence of a comorbidity, 1 point if they receive treatment for the condition, and 1 point if the condition limits their functioning. The maximum score for the full SCQ is thus 45 points.

We plan to use SCQ part 1 comorbidity count (0-15 scale), and the full SCQ (0-45) in separate models. Previous studies have found linear relationships between comorbidity and back-related disability (7, 11), and thus we plan to treat these variables as linear. Linearity with outcome will be assessed, and deviations will be handled appropriately.

Covariates:

Covariates are presented in table 1. They are chosen based on being “established” prognostic factors in the literature, having been utilized in similar studies previously (to enhance comparability), and for being readily available and easy to measure in clinical practice.

Table 1: Covariates, measurement level and/or instrument, rationale for inclusion		
Factor	Measurement level	Rationale
Age	Continuous, minimum age ≥ 55	Standard covariate in previous studies (7, 8, 10), and in some studies reported to be associated with disability levels in older adults (4, 6, 20)
Sex	Dichotomous	Standard covariate in previous studies (7, 8, 10), and in some studies reported to be associated with disability levels in older adults (6, 20)
BMI	Measured continuous, divided into categories: <20, 20-25, 25-30, <35	Covariate in previous study (7), and found to be associated with disability in older adults (4, 21)

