Sensitivity analyses

Complete case analyses will be performed to assess possible bias introduced by the multiple imputation procedures.

Proposed tables and figures

[figure not shown]

Figure: Flowchart of study participants

Baseline characteristics:

Table: Baseline characteristics

Variable	n	Values
Sociodemographic variables		
Age, median (IQR)		
Female, n (%)		
Married or living with partner, n (%)		
Education level high, n (%)		
General health variables		
Health-related quality of life (SF-36), median (range)		
Physical component score		
Mental component score		
Hazardous alcohol consumption (AUDIT-C), n (%)		
Smoking status, n (%)		
Current smoker		
Smoked previously		
Never		
Falls efficacy (FES-I), median (range)		
Back pain history and characteristics of current episode		
First healthcare provider		
General practitioner		
Physical therapist		
Chiropractor		
History of back pain, n (%)		
Using pain medication, n (%)		
Sleep problems weekly due to back pain, n (%)		
Back pain (NRS 0-10) (figure?), median (range)		
Disability (RMDQ 0-24) (figure?), median (range)		
Duration of current episode, n (%)		
0 – 6 weeks		
6 weeks – 3 months		
> 3 months		
Psychological variables		
Kinesiophobia (FABQ-PA 0-28), median (range)		
Depression (CES-D 0-60), median (range)		
Pain catastrophizing (PCS 0-52), median (range)		
Back beliefs and attitudes (BBQ 9-45), median (range)		
Expectations of back pain next 3 months (figure?), n (%)		
Fully recovered		
Much better		
No change or worse		
Psychosocial risk profile (SBT)		
Low risk		
Medium risk		
High risk		
Clinical variables		
Pain with active movements of the back, n (%)		
Positive radiculopathy diagnostic rule, n (%)		
Two or more red flags, n (%)		
Physical performance (BPS), median (range)		
Functional mobility (TUG), median (range)		

SF-36, Short Form health survey 36; AUDIT-C, alcohol use disorders identification test, score ≥ 3 for women and ≥ 4 for men ; FES-I, Falls Efficacy Scale – International; NRS, numeric rating scale; RMDQ, Roland-Morris Disability Questionnaire; FABQ-PA, Fear-Avoidance Beliefs Questionnaire – Physical Activity; CES-D, Center for Epidemiological Studies – Depression; PCS, Pain Catastrophizing Scale; BBQ, Back Beliefs Questionnaire; SBT, Start Back Tool; BPS, Back Performance Scale; TUG, Timed Up-and-Go.

*Comorbidities measured with Self-administered Comorbidity Questionnaire and a question on osteoporosis.

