Persistent back pain = $-4.23 + 0.03 \cdot \text{Age} + 0.73 \cdot \text{Chronic duration} + 0.23 \cdot \text{Back pain intensity} + 0.07 \cdot \text{Disability} + 0.71 \cdot \text{Recent episode} + 0.38 \cdot \text{Spinal morning stiffness} + 0.42 \cdot \text{Pain during spinal rotation} - 0.79 \cdot \text{Recovery expectation}$

Persistent disability = $-5.97 + 0.04 \text{Age} + 0.63 \text{Chronic duration} + 0.32 \text{Disability} + 0.40 \text{Recent episode} + 0.52 \text{Comorbidity} + 0.52 \text{Spinal morning stiffness} - 0.83 \text{Recovery expectation} + 0.08 \text{Depressive symptomology} + 0.02 \text{Pain catastrophizing}$

Persistent self-reported non-recovery = $-3.46 + 0.03 \text{Age} + 0.60 \text{Chronic duration} + 0.13 \text{Disability} + 1.11 \text{Recent episode} + 0.36 \text{Pain during spinal rotation} - 0.95 \text{Recovery expectation}$

Model performance will be measured with calibration-in-the-large (CITL), calibration slope, Nagelkerke's pseudo- R^2 , and Area under Receiver Operator Characteristics curve (AUC). (Table 4 and Figure 1 below.) CITL and calibration slope is assessed through a calibration plot, where observed outcomes are plotted against predicted risks. Perfect calibration is indicated by a CITL value of 0 and a calibration slope value of 1 (14). Nagelkerke's pseudo- R^2 is a measure of overall model performance that ranges between 0 (worst possible performance) and 1 (best possible performance). AUC is a measure of the model's discriminative performance. A value of 1 indicates perfect discrimination and a value of 0.5 indicates discrimination no better than chance. AUC values between 0.7 and 0.8 are considered acceptable, between 0.8 and 0.9 excellent, and between 0.9-1.0 outstanding (25).

Step 3, model recalibration and updating:

If the models perform unsatisfactorily in the validation sample, updating the models may be needed. We will assess several alternatives in a step-by-step manner during this stage, following the frameworks of Debray et al (24) and Steyerberg (14):

1. Adjustment of model intercept, in case of poor calibration-in-the-large.
2. Overall adjustment of the calibration slope, in case of poor calibration slope.

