3. In case of poor discrimination in validation models compared to original models, model revision may be performed. This involves re-estimation of predictor effects, including assessing linearity assumptions of continuous prognostic factors with restricted cubic splines or fractional polynomials. The re-estimated predictor effects will be corrected for over-optimism by applying a uniform shrinkage factor derived from 500 bootstrapped samples.
4. Model extension, introducing new candidate predictors to the model and assess improvement in performance. The candidate predictor to be tested and rationale can be found in Table 2 below.

Table 2: Candidate prognostic factor for model extension.

Candidate prognostic factor	Rationale
Reduced sleep quality attributable to back pain (based on item 5i from PSQI)	Sleep problems are common in older adults (26), and associated with disability in a cross-sectional study on back pain in older adults (27). Reduced sleep quality often co-occurs with chronic pain (28-30).
PSQI: Pittsburgh Sleep Quality Index	

If model performance after completing a step is acceptable, we will not proceed with further steps.

Sensitivity analyses

Complete case analyses will be performed to assess the possible bias introduced from the imputation procedure.

Proposed tables and figures

Baseline characteristics:

Table 3: Patient characteristics and clinical status at baseline in development sample and validation sample.

	Development sample, BACE-D		Validation sample, BACE-N	
	All participants (n=675)	Missing, n (%)	All participants (n=452)	Missing, n (%)
Age, mean (SD)				
Female, n (%)				
BMI, mean (SD)				
Education level high, n (%)				
Employment status currently paid work, n (%)				
Health-related quality of life (SF-36), mean (SD)				
Physical component score				
Mental component score				
Current smoker, n (%)				
Musculoskeletal comorbidity, n (%)				
One or more comorbidities, n (%)				
One or more previous back pain episodes, n (%)				
Recent episode of back pain, n (%)				
Radiating leg pain, n (%)				
Using pain medication, n (%)				
Sleep problems weekly due to back pain, n (%)				
Average back pain intensity last week (NRS, 0-10), mean (SD)				
Disability (RMDQ, 0-24), mean (SD)				
Duration of current episode > 3 months, n (%)				
Kinesiophobia (FABQ-PA, 0-24), mean (SD)				
Depression (CES-D, 0-60), mean (SD)				
Pain catastrophizing (PCS, 0-52), mean (SD)				

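### In the persistent-disability model, the published 0.52 for musculoskeletal comorbidity is applied to comorbidity of any kind, although BACE-N recorded items for a closer proxy

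*Combined protocol and SAP*

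**What the plan says.** The external-validation SAP tests three published models. Only the persistent-disability model has a comorbidity term: musculoskeletal comorbidity, coefficient 0.52. Table 1 of that SAP gives its source as "Modified Dutch version of SCQ" and does not list the conditions it covered.

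Under the heading on changes from development to validation, the SAP says that because the questionnaire versions differ, "we are unable to replicate the exact measurement of" musculoskeletal comorbidity. It substitutes a comorbidity variable, "measured with the SCQ as a binary variable with cut-off at ≥ 1 comorbidity". The equation in Step 2 attaches 0.52 to this variable and leaves the intercept at -5.97. The only sensitivity analysis is a complete-case analysis.

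The SAP on the one-year course of disability (22.03.2021) describes what the same cohort collected. Its section on the prognostic factor lists single yes/no items that include "anemia or other blood disease, cancer, depression, osteoarthritis, rheumatoid arthritis and up to 3 non-specified comorbidities". The footnote to its baseline table reads "Comorbidities measured with Self-administered Comorbidity Questionnaire and a question on osteoporosis", and its prevalence table has a separate osteoporosis row.

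**The concern.** A regression coefficient belongs to the variable it was estimated for. In the published model, patients whose only other condition is, say, high blood pressure or diabetes are in the reference group, and their average risk is already carried by the intercept. The Step 2 equation moves them out of that group by 0.52, and no estimate supports the move.

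The stated reason explains why some substitute is needed. It does not explain why the substitute has to be comorbidity of any kind when joint disease was recorded item by item. No closer proxy is discussed.

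At stake is how the validation result is read. Calibration-in-the-large is a main performance measure, and a poor value leads to the first updating action in Step 3, adjustment of the intercept. Miscalibration that comes from the predictor definition could be taken for poor transportability and carried into an updated model.

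**Working it through.** **Inputs from the documents.** The coefficient is 0.52 and the intercept -5.97, the same in the published and the tested equation. The assumed outcome prevalence is 40% (sample-size section). Neither the prevalence of any comorbidity (p_any) nor that of musculoskeletal comorbidity (p_msk) is given, so both are varied below.

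**1. The plan's own figure.** The SAP gives no figure for the effect of the swap. Its one calculated figure, a minimum sample size of 426, was reproduced as a check. A C-statistic of 0.8 at 40% prevalence converts to a Cox-Snell R² of 0.2528 (binormal model). With 14 parameters and target shrinkage 0.9, n = 14 / [(0.9 - 1) × ln(1 - 0.2528/0.9)] = 425. This agrees within rounding and does not bear on the point.

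**2. One patient with only non-musculoskeletal disease.** exp(0.52) = 1.68.
- Risk 20%: odds 0.25 × 1.68 = 0.42, risk 30%.
- Risk 40%: odds 0.667 × 1.68 = 1.12, risk 53%.
- Risk 50%: odds 1 × 1.68 = 1.68, risk 63%.

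**3. The whole sample.** The rise in the mean linear predictor is 0.52 × (p_any - p_msk).

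| Assumed gap (points) | Rise in linear predictor | Rise in risk at 40% (points) |
|---|---|---|
| 10 | 0.05 | 1.3 |
| 20 | 0.10 | 2.5 |
| 30 | 0.16 | 3.8 |
| 40 | 0.21 | 5.1 |
| 50 | 0.26 | 6.4 |
| 60 | 0.31 | 7.7 |

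The linear approximation, rise × 0.40 × 0.60, gives 2.5 points for a gap of 20 and 6.2 for a gap of 50.

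**4. Which performance measure moves.** A simulation used 400,000 records in each of five scenarios. It took p_msk from 0.3 to 0.6 and p_any from 0.6 to 0.9 (gaps of 30 or 40 points), a standard deviation of 1.2 for the rest of the linear predictor, and no effect of non-musculoskeletal disease.
- With the original construct, calibration-in-the-large was about 0 and the slope about 1.
- With any comorbidity at 0.52, calibration-in-the-large was -0.15 to -0.22, the slope 0.96 to 0.99, and the AUC fell by 0.005 to 0.007.
- The best-fitting coefficient for any comorbidity was 0.24 to 0.36.

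The term is diluted but still informative, and the shift is almost entirely in the average level of predicted risk.

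**The case against.** Several objections stand, and they limit the point.

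- **Disclosure.** A reader might infer that the model is tested with a wrong predictor that went unnoticed. The documents do not support that. The SAP names the swap and gives a reason. What they support is that the predictor is broader than the one the coefficient belongs to.
- **Unknown Dutch items.** No list of the Dutch conditions is given. A proxy from osteoarthritis, rheumatoid arthritis and osteoporosis is closer in construct, but its agreement with the original cannot be shown. If the Dutch variable covered conditions that BACE-N did not ask about, the proxy would under-predict. An assumed shortfall of 10 to 30 points gives 0.52 × 0.10 to 0.52 × 0.30, a shift of -0.05 to -0.16.
- **Other comorbidity may matter.** The disability-course SAP says that the number of comorbidities is associated with the course of disability, while calling its prognostic value uncertain. Part of the +0.52 may therefore be real for the patients who receive it. How far that offsets the average error depends on case mix, because the published intercept already reflects such patients.
- **Discrimination.** A reader might infer that the term loses its discriminating value, or that the swap would trigger re-estimation of the predictors. The AUC loss above, obtained with no effect of other disease assumed, does not support either reading.
- **Other changes to the same equation.** Two negative spline terms (-0.17 disability, -0.08 depression) are dropped. If the disability spline averaged two units (assumption; the knots are not given), that alone adds 0.34. The 60-minute stiffness item, also weighted 0.52, is stricter than the Dutch 30 minutes and pushes the other way. The net calibration error cannot be attributed to comorbidity alone.
- **Table 3.** The row "Musculoskeletal comorbidity, n" stands in a shell shared by both cohorts. A reader might take it as proof that BACE-N has this variable, but it may be meant for the Dutch column only.

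None of this explains why the recorded musculoskeletal items go unused.

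**Conclusion.** The point holds for one model of three. In the persistent-disability model, 0.52 and an unchanged intercept are applied to a broader predictor than the one they were estimated with, while items for a narrower one were collected. For an assumed gap of 20 to 50 points, the mean linear predictor rises by 0.10 to 0.26. The figures in points of risk are upper values if other comorbidity carries risk of its own. The plausible consequence is a contribution to an intercept update in Step 3. The rise follows directly from the equation; its actual size rests on prevalences that the documents do not give, and it acts together with the spline and stiffness changes. This is a modest and avoidable departure that should be corrected. It does not invalidate the validation.

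**What to change.** 1. Predefine a musculoskeletal comorbidity proxy in BACE-N: yes to the SCQ osteoarthritis or rheumatoid arthritis item, or a free-text condition coded as musculoskeletal under a stated rule, blind to outcome. Add the osteoporosis question if the Dutch variable included that condition. Check the definition against the Dutch item list if it can be obtained.
2. Use the proxy with 0.52 in Step 2, report Step 2 performance with any comorbidity alongside, and state that neither is identical to the Dutch item.
3. Reconcile the two descriptions of the questionnaire. The external-validation SAP says a Norwegian version of the original SCQ was used; the disability-course SAP says a modified version with the back-pain item removed. If a back-pain item counted, nearly everyone would have at least one comorbidity and the term would act almost as a constant.

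The PASS prediction-model SAP says the external validation has been done, so a supplementary re-analysis would serve the same purpose. The cost is SAP wording and recoding of items already collected. The downside is a proxy that remains imperfect and some free-text coding.
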